8.2 Handling of Missing Data

Missing data imputation will be done only for efficacy variables (categorical and continuous variables). For the analysis other than efficacy, no imputation will be done for missing values.

Censoring

For the time-to-event endpoint, i.e., time to clinical response per Partial Adapted Mayo score, missing data will be considered as censored at the last available time for the information.

Non-Responder Imputation incorporating Multiple Imputation to handle missing data due to COVID-19 (NRI-C)

The NRI-C will categorize any subject who does not have an evaluation during a pre-specified visit window (either due to missing assessment or due to early withdrawal from the study) as a non-responder for the visit. In addition, at or after the UC-related corticosteroids intercurrent event (see Section 8.1), subjects will be counted as non-responders. The only exception is that missing data due to COVID-19 infection or logistical restrictions related to the COVID-19 pandemic will be handled by Multiple Imputation (MI). At each visit, subjects will be characterized as responders or non-responders based on MI imputed values if missing due to COVID-19; otherwise, subjects will be considered as non-responders for missing due to other reasons in the NRI-C approach.

Mixed-Effect Model Repeated Measurements (MMRM)

MMRM analysis will be conducted using mixed-effect model including observed measurements at all visits. For the MMRM analysis, data collected at or after UC-Related corticosteroids intercurrent event will be excluded. The mixed model includes the categorical fixed effects of visit, baseline corticosteroid use (yes vs no), baseline Mayo endoscopic sub-score (2 vs 3), the continuous fixed covariate of baseline measurement and treatment and treatment-by-visit interaction, if applicable. An unstructured variance covariance matrix will be used. If there is a convergence issue, a compound symmetry structure and a variance components structure will be considered in sequence. The parameter estimations are based on the assumption of data being missing at random and using the method of restricted maximum likelihood (REML).

As Observed (AO)

The AO analysis will not impute values for missing evaluations, and thus a subject who does not have an evaluation on a scheduled visit will be excluded from the AO analysis for that visit. All observed data will be used in the analysis.

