## 5.5 Withdrawal of Subjects and Discontinuation of Study Drug or from Study Participation

---

A subject may voluntarily withdraw or be withdrawn from study participation, or be discontinued from study drug, at any time for reasons including, but not limited to, the following:

- Disease progression or lack of response to treatment.

- Clinically significant abnormal laboratory results or AEs, which rule out continuation of the study drug, as determined by the investigator or the AbbVie TA MD.
- The investigator believes it is in the best interest of the subject.
- The subject requests withdrawal from the study. This includes if a subject would like to discontinue after completion of the Week 52 visit.
- Eligibility criteria violation was noted after the subject started study drug and continuation of the study drug would place the subject at risk.
- Introduction of prohibited medications or dosages and continuation of the study drug would place the subject at risk.
- The subject becomes pregnant while on study drug.
- Subject has a malignancy, except for localized non-melanoma skin cancer. Discontinuation for carcinoma in situ of the cervix is at the discretion of the Investigator.
- Subject is significantly noncompliant with study procedures, which would put the subject at risk for continued participation in the trial.

Subjects who complete the induction period and do not achieve clinical response per Partial Adapted Mayo score at Week 12 will be discontinued.

For subjects to be considered lost to follow-up, reasonable attempts must be made to obtain information on the subject's final status. At a minimum, 2 telephone calls must be made and 1 certified letter must be sent and documented in the subject's source documentation.

AbbVie may terminate this study prematurely, either in its entirety or at any site. The investigator may also stop the study at his/her site if he/she has safety concerns. If AbbVie terminates the study for safety reasons, AbbVie will promptly notify the investigator.

During states of emergency or pandemic situations, it may be necessary to employ mitigation strategies to enable the investigator to ensure subject safety and continuity of care. Acceptable mitigation strategies are identified and included in the Operations Manual in [Appendix F](#).

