3.2 Secondary Endpoints

- Clinical remission per Adapted Mayo score at Week 8

- Clinical response per Adapted Mayo score at Week 8
- Clinical response per Partial Adapted Mayo score over time (Week 0 to 12)
- Clinical remission per Full Mayo score at Week 8 in subjects with a Full Mayo score of 6 to 12 at Baseline
- Endoscopic remission at Week 8

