3.3 Additional Efficacy Endpoints

Additional efficacy endpoints are:

- Change from Baseline in modified Baron score over time (at visits with endoscopy)
- Achievement with stool frequency subscore (SFS) = 0, rectal bleeding subscore (RBS) = 0, and Mayo endoscopic subscore = 0 over time (at visits with endoscopy)
- Time to clinical response per Partial Adapted Mayo score
- Endoscopic improvement over time (at visits with endoscopy)
- Clinical remission per Adapted Mayo score over time (at visits with endoscopy)
- Clinical response per Adapted Mayo score at over time (at visits with endoscopy)
- Clinical remission per Partial Adapted Mayo score over time
- Clinical response per Partial Adapted Mayo score over time
- Clinical remission per Adapted Mayo score over time among subjects who were taking corticosteroids at Baseline and subsequently discontinued corticosteroids for \geq 90 days prior to the respective visit
- Discontinuation of corticosteroid use for subjects taking corticosteroids at Baseline at all visits over time
- Endoscopic remission over time (at visits with endoscopy)
- Clinical remission per Full Mayo score over time in subjects with a Full Mayo score of 6 to 12 at Baseline (at visits with endoscopy)
- Clinical response per Full Mayo score over time in subjects with a Full Mayo score of 6 to 12 at Baseline (at visits with endoscopy)

- Achievement of SFS ≤ 1 over time
- Achievement of RBS = 0 over time
- Change from Baseline in RBS over time
- Change from Baseline in SFS over time
- Change from Baseline in fecal calprotectin (FCP) over time
- Change from Baseline in high sensitivity C-reactive protein (hs-CRP) over time
- Change from Baseline in Inflammatory Bowel Disease Questionnaire (IBDQ) over time
- UC-related Hospitalizations (yes/no) over time
- UC-related surgeries (yes/no) over time
- No bowel urgency over time
- Change from Baseline in weekly abdominal pain score over time
- Achievement of $\geq 30\%$ reduction from Baseline in weekly abdominal pain score over time
- Achievement of Weekly abdominal pain score = 0 over time
- Change from Baseline in number of extraintestinal manifestations (EIM) over time (as captured in the EIM electronic case report form [eCRF])
- Histologic remission over time (at visits with endoscopy)
- Mucosal healing (endoscopic and histologic remission) over time (at visits with endoscopy)

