8.0 Efficacy Analyses

8.1 General Considerations

UC-Related corticosteroids intercurrent events are defined as follows:

- subjects not on UC-related corticosteroids (systemic or locally acting corticosteroids for UC) at Baseline who initiated UC-related corticosteroids during the Induction Period;
- subjects on UC-related systemic corticosteroids at Baseline who had dosages increased to greater than the prednisone equivalent dose of corticosteroid at Baseline, or initiation of any rectal corticosteroids during the Induction Period regardless of rectal corticosteroid dose.

The time point of the UC-related corticosteroids intercurrent event is defined as the date when one of the scenarios above occurs for a subject. As such, subjects will be considered as "non-responder" for binary endpoints at or after the occurrence of the UC-related corticosteroids intercurrent event through the end of the Induction Period. For continuous endpoints, all measurements at or after the occurrence of the UC-related corticosteroids intercurrent event through the end of the Induction Period will not be used in the analysis.

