8.5 Additional Efficacy Analyses

Additional endpoints defined in Section 3.3 will be summarized at scheduled time points.

Additional Efficacy Analyses for Induction Period

For additional binary endpoints, point estimate and 95% CI using normal approximation will be provided for the response rate of the ravagalimab group using NRI-C and AO data.

For additional continuous endpoints, the LS-mean and 95% CI will be reported for the ravagalimab group using MMRM model and ANCOVA model based on AO data with baseline corticosteroid use (yes vs no) and baseline Mayo endoscopic sub-score (2 vs 3) as the fixed factors and the corresponding baseline value as the covariates.

For selected additional binary endpoints, point estimate and 95% CI using normal approximation will be provided for the response rate of ravagalimab and matched placebo group. Point estimate, 95% CI and p-value will be provided for the treatment comparison between ravagalimab and the matched placebo group based on the CMH test adjusting for baseline corticosteroid use (yes vs no) and Mayo endoscopic sub-score (2 vs 3).

For selected additional continuous endpoints, the LS mean and 95% CI will be reported for ravagalimab and matched placebo group. The LS mean treatment difference and associated 95% CI and p-values between ravagalimab and matched placebo group will be provided using MMRM model. For the MMRM analysis, data collected at or after UC-Related corticosteroids intercurrent event will be excluded. Supplementary analysis will be conducted based on ANCOVA model using AO data, with treatment, baseline corticosteroid use (yes vs no) and baseline Mayo endoscopic sub-score (2 vs 3) as the fixed factors and the corresponding baseline value as the covariates.

Additional Efficacy Analyses for Maintenance Period

Descriptive statistics will be provided for the ravagalimab group. These include the number of observations, mean, standard deviation, 95% CI, median, minimum, and maximum for continuous endpoints using AO data; and frequencies and percentages with 95% CI using normal approximation for binary endpoints using AO data.

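### Time to clinical response is censored whatever the reason for missing data and has no stated steroid rule, unlike the same response analysed by visit

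*SAP*

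**What the plan says.** SAP 3.3 lists "Time to clinical response per Partial Adapted Mayo score" among the additional efficacy endpoints. SAP 8.2, under Censoring, gives its only missing-data rule: "time to clinical response per Partial Adapted Mayo score, missing data will be considered as censored at the last available time for the information". The rule applies to every reason for missing data.

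The same response by visit, Weeks 0 to 12, is a secondary endpoint (SAP 3.2), analysed with NRI-C and as observed (SAP 8.4). Under NRI-C a subject without an evaluation in the visit window is a non-responder for that visit, including after early withdrawal. COVID-19-related missing data are the exception and are multiply imputed. NRI-C also has a steroid rule: "at or after the UC-related corticosteroids intercurrent event (see Section 8.1), subjects will be counted as non-responders".

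SAP 8.1 sets out that steroid rule by endpoint type. Subjects are non-responders "for binary endpoints at or after the occurrence of the UC-related corticosteroids intercurrent event through the end of the Induction Period". The continuous rule begins "For continuous endpoints, all measurements at or after the occurrence of the UC-related corticosteroids intercurrent event" and excludes those measurements from analysis. Neither sentence mentions the time-to-event endpoint. SAP 8.5 says "Additional endpoints defined in Section 3.3 will be summarized at scheduled time points" and then gives methods for binary and continuous endpoints only, so no estimator is named for time to response.

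Protocol 5.5 lists "Disease progression or lack of response to treatment" among the reasons for stopping study drug or leaving the study. Protocol 5.6 asks that subjects who stop drug keep attending scheduled visits unless they withdraw consent.

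**The concern.** Censoring at the last available time is harmless when the subjects who leave would have gone on to respond at the same rate as those who stay. Here lack of response is itself a listed reason to go, so some leavers are likely to be worse than those still followed. A standard survival estimator would give them the response chance of subjects still at risk, and the error favours the drug.

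The second gap is steroid rescue. Nothing says whether a first response recorded after the steroid intercurrent event is an event in this analysis. Two programmers could decide differently.

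On both counts the handling differs, or may differ, from NRI-C for the same response definition at the same visits. What is at stake is the description of how quickly and how often subjects first respond. That is part of the time-course Protocol 4.1 sets out to explore by following subjects to Week 12.

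**Working it through.** The documents state no event count, median, drop-out rate or rescue rate for this endpoint, so there is no planned figure to reproduce. The figures below are illustrations.

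**Inputs from the documents.** N = 40 (SAP 2.4). Post-baseline Partial Adapted Mayo assessments in induction fall at Weeks 2, 4, 8 and 12 (Operations Manual 2.1).

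**Assumptions.** A Kaplan-Meier estimator; 16 observed first responders; all leavers are non-responders who would not have responded; events precede censorings at the same visit.

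**Formulas.** With d responses and c censorings at visit j and n at risk:
- Leavers censored: 1 − Π(1 − d_j/n_j), with n_(j+1) = n_j − d_j − c_j.
- Leavers kept as non-responders: the same product with n_(j+1) = n_j − d_j, which reduces to total responders / N = 16/40 = 40.0%.

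With no leavers both give 40.0%.

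**One case in full.** Four responses at each visit; 2, 3 and 3 subjects leave after Weeks 2, 4 and 8. The risk sets are 40, 34, 27 and 20:

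1 − (36/40)(30/34)(23/27)(16/20) = 45.9%, which is 5.9 points above 40.0%.

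In subjects: 0.4588 × 40 = 18.35, or about 2.4 more than the 16 observed.

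**Other patterns** (reference value 40.0% throughout):

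| Leavers after Weeks 2, 4, 8 | Responses 4, 4, 4, 4 | Responses 2, 4, 5, 5 |
|---|---|---|
| 4 (1, 1, 2) | 42.4% | 42.8% |
| 4 (2, 2, 0) | 43.3% | 43.7% |
| 8 (2, 3, 3) | 45.9% | 46.8% |
| 8 (4, 4, 0) | 47.5% | 48.4% |
| 12 (4, 4, 4) | 50.8% | 52.2% |

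The excess is about 2 to 4 points with 4 leavers, 6 to 8 with 8, and 11 to 12 with 12.

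**A second case at a higher response rate.** 8 of 40 respond by Week 4, 6 leave without a response, and 12 of the remaining 26 respond: 1 − (32/40)(14/26) = 56.9%, against 20/40 = 50%.

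**Steroid rescue.** One response counted or not counted moves the crude proportion by 1/40 = 2.5 points. If 1, 2 or 4 of the 16 responses followed rescue, leaving them out gives 15/40 = 37.5%, 14/40 = 35.0% or 12/40 = 30.0%.

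**What alignment cannot do.** Suppose 20 of 40 respond at some point and 3 of them have lost response by Week 12. The cumulative figure is 20/40 = 50%; the Week 12 rate is 17/40 = 42.5%. The two differ with nobody leaving.

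**The case against.** The case against giving this weight is substantial, and much of it stands.

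- A reader might infer that leavers are counted as future responders. They are not. In the case worked in full, 8 leavers add about 2.4 responders; counting all 8 would give 24/40 = 60%. Even the smaller effect needs a Kaplan-Meier-type estimator, which the SAP does not name.
- A reader might infer that responses after rescue do count as events. The SAP is silent on this. Visit-level response is a binary endpoint, so a time to first response derived from it could inherit the non-responder rule of SAP 8.1. Steroid initiation is also prohibited through Week 12 (Protocol 5.3), which should keep such cases few.
- A reader might infer that the censoring rule is why the curve and the Week 12 NRI-C rate would differ. A cumulative first-response curve can exceed a visit-level rate simply because subjects lose response.
- Protocol 5.6 keeps subjects who only stop drug in follow-up, so stopping for lack of response does not by itself cause missing data. The illustrations assume that only non-responders leave, which is the unfavourable extreme.
- A crude repair could do harm. Making anyone with one missed visit, or anyone who stops drug, a permanent non-responder would erase later observed responses that NRI-C keeps.

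These points limit the size of the problem and shape the fix. They do not remove the core. Subjects can still leave the study entirely, lack of response is a listed reason, and nothing else in the SAP corrects a rule that censors them regardless of reason.

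**Conclusion.** The point holds as a minor one. The censoring rule in SAP 8.2 ignores the reason for missing data, and the steroid rule is not stated for this endpoint. If non-responders leave and a Kaplan-Meier-type estimator is used, the curve is biased upward, by about 2 to 4 points with 4 of 40 leaving and 6 to 8 with 8. Post-rescue responses, if counted, add 2.5 points each to the crude proportion. These sizes rest on assumed response patterns and on leavers who would not have responded; the actual drop-out and rescue rates are not in the documents.

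The reach is small. This is one additional endpoint in a single-arm exploratory study, and no primary or secondary result depends on it. Subjects who enter maintenance have responded at Week 12 and those without a response are discontinued (Protocol 4.1), so the issue lies almost wholly in induction.

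**What to change.** In SAP 8.2 and 8.5:

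1. Name the estimator for time to clinical response.
2. Keep in the risk set, as non-responders censored at Week 12, subjects who leave the study without a response for non-COVID reasons and subjects who have the steroid intercurrent event before responding. Treating both as competing events and reporting cumulative incidence is an alternative; it gives the same figure when nobody is censored for COVID-19 before Week 12.
3. State that a response at or after the steroid event during induction does not count.
4. State that an intermittently missed visit is non-response for that visit only. Observed responses at later attended visits, including visits after stopping study drug, still count unless item 3 applies.
5. Reserve censoring at the last available assessment for follow-up lost for COVID-19-related reasons.

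This brings the handling of leavers and rescue into line with NRI-C. It does not make the cumulative curve equal the Week 12 NRI-C rate, and the SAP should say so to prevent misreading. The cost is a few lines of text and one derivation, with no new data; the reported curve may be a few points lower.

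### If the unstructured MMRM does not converge, the SAP's last fallback removes within-subject correlation and with it the stated missing-at-random basis; compound symmetry before it is sound only if its form holds

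*SAP*

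**What the plan says.** The MMRM paragraph of SAP 8.2 starts from the most general structure: "An unstructured variance covariance matrix will be used". The fallback is: "If there is a convergence issue, a compound symmetry structure and a variance components structure will be considered in sequence". The next sentence gives the basis of inference: "The parameter estimations are based on the assumption of data being missing at random", with REML. No degrees-of-freedom method and no robust variance is named.

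The plan also creates missing values. For continuous endpoints, SAP 8.1 says that "all measurements at or after the occurrence of the UC-related corticosteroids intercurrent event through the end of the Induction Period will not be used", and SAP 8.2 repeats this for the MMRM.

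Under SAP 8.5 the model serves the additional continuous endpoints of the Induction Period. It gives the ravagalimab LS-mean and 95% CI, beside an ANCOVA on as-observed data. For selected endpoints it also gives a comparison: "The LS mean treatment difference and associated 95% CI and p-values between ravagalimab and matched placebo group will be provided using MMRM model". The primary endpoint uses a Bayesian analysis with NRI-C (SAP 8.3), the secondary endpoints are all binary (SAP 3.2), and maintenance data are described only.

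**The concern.** An MMRM is valid under missing at random because the correlation between visits carries information from a subject's earlier values to the visits that are missing. A fallback that sets this correlation to zero removes that mechanism but leaves the claim standing. Values removed after a steroid event, and withdrawal for lack of response (Protocol 5.5), can both depend on earlier poor values, so this kind of missingness is plausible here.

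Both fallback structures also impose one variance on all visits. If the spread differs between visits, the standard error is too small at some visits and too large at others. Late-visit LS-means and intervals for endpoints such as stool frequency, rectal bleeding and hs-CRP would be affected, as would the standard errors of the matched-placebo differences.

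**Working it through.** **1. What each structure estimates.** With V post-baseline visits:
- Unstructured: V(V+1)/2 parameters, so 10 for V = 4 and 3 for V = 2.
- Compound symmetry (CS): 2, one variance and one correlation.
- Variance components (VC) as a residual structure, σ²I: 1, with correlation zero. If VC instead means a random subject intercept, it equals CS with a non-negative correlation, and a CS failure is followed by essentially the same model.
- Heterogeneous AR(1) and heterogeneous CS: V + 1 = 5 for V = 4. Heterogeneous Toeplitz: V + (V − 1) = 7.
- For V = 2 every heterogeneous structure has 2 + 1 = 3 parameters, as many as unstructured.

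**2. Where structure matters.** By the visit lists in Operations Manual 2.1, SFS, RBS and hs-CRP have four post-baseline induction visits (Weeks 2, 4, 8, 12). IBDQ, FCP and extraintestinal manifestations (assessed at physical examination) have two (Weeks 8, 12). Endoscopic scores have one, so structure has no effect on them.

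**3. Missing at random under VC.** With zero correlation, the visit mean is the covariate-adjusted mean of subjects observed at that visit. Its bias is E(Y_t | observed at t) − E(Y_t). This is not zero when being observed depends on earlier values and those values are in truth correlated with Y_t. A robust standard error does not change it.

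**4. Common variance.** Take SDs of 0.7, 0.9, 1.2, 1.4 (assumed). The pooled variance is (0.49 + 0.81 + 1.44 + 1.96)/4 = 1.175, so the pooled SD is 1.08. The ratio to the true SD is 1.08/1.4 = 0.77 at Week 12 and 1.08/0.7 = 1.55 at Week 2. A ratio of 0.77 turns ±1.96 into ±1.52, or about 87% coverage; a ratio above 1 over-covers. Reversing the SDs reverses the visits.

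**5. Simulation.** The documents give no SD, correlation or dropout rate for these endpoints, so there is no plan figure to reproduce and all such inputs are assumptions. Setting: single arm, n = 40, four visits, the SAP's covariates, REML, 600 runs. Dropout, where present, depends on the previous value (about 25% lost by Week 12). Monte Carlo error is √(0.95 × 0.05/600) = 0.9 points near 95% and √(0.66 × 0.34/600) = 1.9 points near 66%. Week 12 coverage of the 95% CI, with bias in brackets:

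| Scenario | Unstructured | CS | VC |
|---|---|---|---|
| Equal SD, r = 0.6, complete | 96.0% | 96.8% | 94.2% |
| Equal SD, r = 0.6, dropout | 95.3% | 96.2% (+0.01) | 85.3% (−0.18) |
| SD 0.7 to 1.4, AR(1) 0.8, complete | 95.7% | 91.2% | 87.3% |
| SD 0.7 to 1.4, AR(1) 0.8, dropout | 93.5% | 85.8% (−0.11) | 66.2% (−0.27) |
| SD 1.4 to 0.7, AR(1) 0.8, complete | 94.3% | 99.5% | 98.8% |

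In the rising-SD complete-data row, Week 2 coverage is 99.5% (CS) and 98.2% (VC), so both structures over-cover there.

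**6. Other assumptions.** With r = 0.6, about 19% excluded after Week 4 according to the Week 4 value, and 500 runs, Week 12 coverage for VC, CS and heterogeneous CS was 88%, 94%, 94% with equal SDs; 78%, 90%, 95% with SDs 0.8 to 1.2; and 74%, 83%, 94% with SDs 0.6 to 1.2.

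**7. Replacement structures.** In separate runs with rising SDs, AR(1) 0.8 and about 23% dropout, Week 12 coverage was VC 66% (−0.25), CS 82% (−0.10), heterogeneous CS 92% (+0.05) and heterogeneous AR(1) 93% (+0.01). With equal SDs and dropout, VC gave 86% and CS 95%; the heterogeneous pair gave 95% and 94%. Heterogeneous Toeplitz and corrected empirical errors were not simulated.

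**The case against.** The trigger may never occur. Unstructured is fitted first and needs at most 10 covariance parameters from about 40 subjects. In 300 simulated data sets (SD 0.6 to 1.2, r = 0.6, about 18% lost after Week 4, normal data, not SAS) the unstructured fit failed 0 times. Skewed or sparse endpoints could behave worse, but no failure rate has been shown. This stands, and it is the main reason the point is minor.

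The missingness may be lighter than simulated. Protocol 5.3 and 5.4 prohibit starting or increasing corticosteroids through Week 12, so steroid exclusions should mostly be deviations, and Protocol 5.6 asks subjects who stop study drug to keep attending visits. This lowers the likely bias but does not make the last step coherent with its paragraph.

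CS is a legitimate simplification, and for two-visit endpoints it is the only real one, because the heterogeneous structures save no parameters there. This also stands, so CS should stay.

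The ANCOVA beside the MMRM is a weaker safeguard. If run by visit it imposes no common variance, but it too uses only subjects seen at that visit and so shares the missing-data bias.

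A reader might infer that the MMRM comparison with matched placebo would be tilted toward ravagalimab. The material does not show that. With one exclusion model in both arms, the VC bias in the Week 12 difference was about 0 when the means were equal. It was +0.04 to +0.07 against ravagalimab when the placebo change was assumed to be −0.7 to −0.4.

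**Conclusion.** The concern holds in a narrow form. The VC step either contradicts the stated missing-at-random basis (residual reading) or is redundant after CS (random-intercept reading). On the residual reading with outcome-dependent dropout, Week 12 coverage was 85–88% with equal SDs and 66–78% with rising SDs. The single-arm bias was negative, which flatters ravagalimab where lower values are better and poor responders are the ones lost.

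Two stronger readings are tempting and not supported. The first is that both fallbacks make intervals under-cover in general. CS was nominal when variances were equal, and either structure over-covers at visits whose variance is below the pooled value. The second is that CS also gives up missing at random. It keeps within-subject correlation and is valid if its form holds; when its form is wrong it was biased, but by less than VC.

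The sizes rest on assumed SDs, correlations and dropout. The issue is limited to additional continuous induction endpoints with at least two post-baseline visits whose unstructured fit fails. It does not touch the primary or secondary endpoints. Priority: minor.

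**What to change.** Replace the fallback sentence in SAP 8.2 along these lines:
- If the unstructured model does not converge and the endpoint has three or more post-baseline induction visits, fit heterogeneous Toeplitz, then heterogeneous AR(1), then heterogeneous compound symmetry, with Kenward-Roger degrees of freedom.
- If none converges, or the endpoint has two such visits, use homogeneous compound symmetry with small-sample-corrected empirical standard errors. State that these correct the interval but not bias from missing data.
- Delete the variance components step.
- Report which structure was used for each endpoint.

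Cost: one SAP sentence and a program option before the primary database lock, with no effect on conduct or sample size. At four visits the heterogeneous structures use 5 to 7 covariance parameters instead of 2, and intervals at high-variance visits become somewhat wider. With equal variances the loss in the simulations was at most about 1 point of coverage.
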